#### **Phase II**

Once the initial phase is complete, the phase II will open to allow for a total accrual of 24 patients.

We estimate accrual of an average of 4 patients per month, with a goal of completing accrual within 12 months.

Based on an optimal 2 - stage design, we can test the null hypothesis that the overall response rate is  $\leq 25\%$  versus the alternative that the overall response rate is  $\geq 50\%$ . If the combination is actually not effective, there is a 0.049 probability of concluding that the combination is effective (target alpha = 0.05); if the combination is actually effective, there is a 0.2 probability of concluding that it is ineffective (power = 80%). With 9 patients treated in the first stage, if 2 or fewer patients have a response within a stratum, the trial will be terminated. If the trial continues to the second stage, an additional 15 patients will be studied. If 9 or fewer patients respond by the end of the second stage, the combination will not be considered for further study. The total number of patients studied will be 24. The probability of early

stopping for this trial is 0.60. The expected sample size when the true response rate is 0.25 is 15.

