### 2.3.7 Efficacy of Romidepsin

Positive results were reported in 71 patients with CTCL treated on the multicenter NCI study of romidepsin administered as a 4-hour infusion on days 1, 8, and 15 of a 28-day cycle with a starting dose of 14 mg/m^2[19]. The ORR was 34%, with a CR observed in four patients, a PR in 20, and SD in 26. The median time to progression for patients with a major response (CR or PR) was 15.1 months.

Very encouraging responses have also been reported in patients with peripheral T-cell lymphoma (PTCL). ORR of 31%, as a single agent in 48 patients, including four CR and 11 PR [25]. The overall median duration of response for all patients was 9 months.

[figure not shown]
In 2011, the US FDA approved romidepsin for patients with relapsed/refractory PTCL.

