## 2.4 Rationale for the Study

### 2.4.1 Hypothesis and Preliminary Data

Targeting HDAC's in patients with TCL has proven to be a valuable therapeutic approach [7]. Vorinostat became the first HDACi approved for the treatment of cancer, for patients with relapsed and refractory CTCL in 2006, followed in 2009 by the approval of romidepsin and expanded in 2011 to include patients with relapsed and refractory PTCL. The promising experience with HDACi in T-cell lymphoma, driven by empirical observations, established that targeting the 'epigenome' was a viable treatment strategy for select sub-types of lymphoma, albeit, effective in about one-third of all TCL patients [9]. Experiences from myeloid leukemia and myelodysplastic syndrome have suggested that combinations of epigenetically targeted drugs, including HDACi plus hypomethylating agents (HoMe), may have more therapeutic value than either of these agents alone. In addition, **HDACi shown to decrease DNMT-1**, leading to reduced genomic methylation and gene activation [15]. These data suggest that the overlapping influences HDACi and HoME on the epigenome could be exploited in rational combinations.

[figure not shown]
To date we have evaluated these two drug classes combination in a variety of preclinical models of cell lymphoma, [16], and have explored the influence of the individual drugs and their combination on gene expression in different sub-types of T-cell lymphoma. These data revealed substantial synergism between the hypomethylating agents (*decitabine and 5-azacitidine*) and various *HDACi including romidepsin, belinostat, vorinostat and panobinostat* with synergy coefficients ranging between 0.1 and 0.9 (see Figure below) [17]. While the synergy seen here was observed following a modest (~12 hr) lead in of the HoMe agent, it suggests a class effect between the different HDACi and the HoMe agent, where the IC10-20 of each drug against the specific cell line was used in the combination. These data also underscore the fact that there are many variables that determine

this degree of synergy, including the particular drug-drug combination, drug concentration, schedule and duration of exposure.

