## **PTCL and other T-cell Lymphomas**

The activity of romidepsin was evaluated in a Phase 2, NCI-sponsored study in 48 subjects with PTCL or other T-cell lymphomas. Of these 48 subjects, 28 had PTCL and 20 had other T-cell lymphomas, including angioimmunoblastic, primary cutaneous large T-cell, gamma-delta T-cell, and anaplastic large T-cell lymphomas.

Among all 48 subjects, the ORR (CR+PR) was 31% (15/48). The CR and PR rates were 8% (4/48) and 23% (11/48), respectively. Fifteen percent (15%; 7/48) of subjects experienced stable disease. When response was evaluated among the 34 subjects who received  $\geq$ 2 cycles of therapy, the ORR was 44% (15/34) and the CR and PR rates were 12% (4/34) and 32% (7/34), respectively. Twenty-one percent (7/34) of subjects who received  $\geq$ 2 cycles of therapy experienced stable disease.

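### Does the phase II design need changing because its 25% null lies below every response rate the protocol cites for romidepsin alone?

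*Combined protocol and SAP*

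**What the plan says.** Section 13.2 (Phase II) describes an optimal two-stage design. Nine patients enter first, and the trial stops if two or fewer respond. Otherwise 15 more are treated, for 24 in all. The final rule is: "If 9 or fewer patients respond by the end of the second stage, the combination will not be considered for further study". The null is a response rate of at most 25% and the alternative at least 50%. The error statement is "If the combination is actually not effective, there is a 0.049 probability of concluding that the combination is effective", with power given as 80%. The section then gives the early-stopping probability ("stopping for this trial is 0.60") and, in the next sentence, "The expected sample size when the true response rate is 0.25 is 15".

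The background cites these results for romidepsin given alone:

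- Section 7.2.2.4, PTCL and other T-cell lymphomas: "Among all 48 subjects, the ORR (CR+PR) was 31% (15/48"), and on the make-up of that series, "Of these 48 subjects, 28 had PTCL and 20 had other T-cell lymphomas".
- Section 2.3.7, the 71-patient CTCL study: "The ORR was 34%, with a CR observed in four patients, a PR in 20, and SD in 26".
- Section 7.2.2.4, pooled CTCL: 41% (55/135) of evaluable subjects.

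Section 2.4.1 describes HDAC-inhibitor treatment as a viable strategy, "albeit, effective in about one-third of all TCL patients". That is a remark about the class and is not stated as a response rate.

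Section 1.4 makes estimation of the response rate the phase II primary objective. Section 13.3 plans exact 95% confidence intervals and defines response as the best response by four cycles.

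**The concern.** Every phase II patient receives romidepsin, and section 2.4.1 presents the combination as a possible improvement on HDAC inhibitors alone. A reader could therefore take an ineffective combination to mean one that does no better than romidepsin. The 0.049 does not describe that state if romidepsin alone gives more than 25%, and every whole-series figure the protocol cites is higher. No reason for 25% appears in the text available for review (a few pages were not). The 0.60 carries no condition in its own sentence.

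What would be at stake is the step at 10 of 24. If the rate on romidepsin alone were 31%, about one trial in six of a combination in which azacitidine contributed nothing would go forward. The stage 1 safeguard would also be weaker than it reads.

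**Working it through.** **Inputs.** From section 13.2: n1 = 9, stop at 2 or fewer; n2 = 15; pass at 10 or more of 24; p0 = 0.25, p1 = 0.50. From sections 2.3.7 and 7.2.2.4: 31% (15/48), 34%, 41%. All calculations treat the 24 patients as one group.

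**Formulas.** With X1 ~ Bin(9, p) and X2 ~ Bin(15, p):

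- P(early stop) = P(X1 ≤ 2)
- P(pass) = Σ over x = 3 to 9 of P(X1 = x) × P(X2 ≥ 10 − x)
- E[N] = 9 + 15 × (1 − P(early stop))

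**Reproducing the plan's figures at p = 0.25.**

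- P(early stop) = 0.0751 + 0.2253 + 0.3003 = 0.6007.
- E[N] = 9 + 15 × 0.3993 = 14.99.
- P(pass), terms x = 3 to 8: 0.0132 + 0.0173 + 0.0122 + 0.0047 + 0.0009 + 0.0001 = 0.0484 from rounded terms; unrounded 0.0485.
- At p = 0.50, P(pass) = 0.8055.

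These match the stated 0.60, 15 and 80%. The stated 0.049 differs from 0.0485 by at most 0.0005, which is immaterial and below the 0.05 target. A search over two-stage designs for these hypotheses returns the same optimal design.

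**Same formulas at the cited rates.**

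| True response rate | P(pass) | P(early stop) |
|---|---|---|
| 25% | 0.0485 | 0.601 |
| 31% | 0.162 | 0.436 |
| 15/48 = 31.25% | 0.169 | 0.430 |
| one-third | 0.229 | 0.377 |
| 34% | 0.251 | 0.361 |
| 41% | 0.509 | 0.213 |
| 50% | 0.806 | 0.090 |

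**How firm is 31%?** The exact 95% interval for 15/48 is 18.7% to 46.3%, which contains 25%. Across that interval P(pass) runs from about 0.7% to 70%.

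**What a bare pass shows.** The exact 95% interval for 10/24 is 22.1% to 63.4%. At 12/24 the lower limit is 29.1%. The interval planned in section 13.3 would therefore itself show that a result near the cut-off does not exclude 31%.

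**What a 31% null would cost at 24 patients.** Keep the stage 1 rule and replace 10 by c in the P(pass) formula:

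| c | P(pass) at 31% | P(pass) at 50% |
|---|---|---|
| 10 | 0.162 | 0.806 |
| 11 | 0.086 | 0.705 |
| 12 | 0.039 | 0.569 |

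Holding the error at 31% below 0.05 takes a cut-off of 12, and power at 50% falls from 0.81 to 0.57.

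**The case for a change.** The strongest case for acting is that it costs only wording. A null with no stated reason, set below every benchmark in the same document, invites a reader to give a pass more weight than it can bear. Section 13.2 conditions the expected sample size on 0.25 but not the adjacent 0.60. Uncertainty about 31% is a reason to show operating characteristics over a range.

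Part of this stands. The rationale is missing from the text available, and 25% is below all the cited whole-series rates.

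The rest is weaker. The null is defined in the sentence just before the 0.049, so the meaning of an ineffective combination is fixed there. The 0.60 and the expected sample size are linked arithmetically: 9 + 15 × (1 − 0.60) = 15, so both belong to 25%.

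Nor is 31% established as the right reference. Section 3.1.1 admits untreated patients and CNS involvement, with no limit on prior therapies. The CTCL rates come from a different disease group, and the 41% counts evaluable subjects only. The 71-patient CTCL study gave romidepsin three times per 28 days, against three per 35 here, and the schedule of the 48-patient series is not given. Four cycles here last 4 × 35 = 140 days, while section 7.2.2.4 notes some CTCL responses after six months or more. These differences do not all point the same way.

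Naming 13/24 (lower limit 32.8%) as the first result to exclude 31% would be unsafe. It treats 31% as known, whereas 13/24 against 15/48 gives a two-sided Fisher p of 0.076. It also ignores the two-stage sampling and encourages a cross-study claim the protocol does not make.

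**Conclusion.** No change to the plan is needed. The operating characteristics are correct for the null that section 13.2 states. The 0.16 and 0.44 are the pass and early-stopping probabilities at a rate outside that null; they do not replace 0.049 and 0.60. The choice of 25% is a defensible trade-off. It lies inside the interval for the most relevant cited series, and moving to 31% with 24 patients would cut power at 50% from 0.81 to about 0.57. Followed as written, a pass supports a response rate above 25% and further study of the combination, which is all the protocol says it will do. The planned exact interval shows how much more, if anything, the data support.

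The remaining gap is one of reporting: a reason for 25%, and perhaps a line giving the probabilities at 31%. Supplying these would leave the sample size, cut-offs and analysis as they are. This conclusion rests on the 24 patients being analysed as one group and on no claim of benefit over romidepsin being drawn from crossing 10 of 24.

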#### Tests

Safety evaluations on Day 1

Laboratory Evaluations Days 1, and each day of romidepsin

CT scans at the end of cycles 2 and 6. Then CT scans q3-6 months, until disease progression or initiation of new therapy.  
(PET/CT is optional)

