### **1.4 Phase II Primary Objectives**

- Estimate the ORR (complete + partial response) of the combination of oral 5-azacitidine and romidepsin in patients with relapsed/refractory T-Cell Lymphoma.

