#### 11.1.1 Definitions

Evaluable for toxicity. All patients will be evaluable for toxicity starting from Day 1 of Cycle 1.

Evaluable for objective response. Patients who have received at least one day of therapy, and have had their disease re-evaluated will be considered evaluable for response. These patients will have their response classified according to the definitions stated below. Patients who exhibit objective disease progression prior to the end of cycle 1 will also be considered.

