### **13.3 Analysis of Secondary Endpoints**

#### **Phase I**

The maximum number of cycles will be described by dose level.

The number of delays >7 days will be described at the MTD.

ORR as defined by the guidelines of the International Harmonization Project Group 2007 Revised Response Criteria, and will be tabulated by dose level. (See Section 11.2.1.) Response rates will be based on all patients who receive at least one day of medication.

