#### **Phase II and Exploratory Cohort**

Primary Objective: To estimate ORR defined as best response by 4 cycles.

Disease and patient characteristics at baseline will be summarized using descriptive statistics. For qualitative variables, frequency distributions and proportions will be provided; for quantitative variables, summary statistics (e.g., mean, median, quartiles, standard deviations, etc) and graphical displays (e.g., box plots). Overall response rates will be estimated upon completion of the study along with exact 95% confidence intervals.

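### The Phase II primary ORR and its exact confidence interval have no stated denominator; applying section 11.1.1 would bias the reported ORR upward

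*Combined protocol and SAP*

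**What the plan says.** Section 1.4 makes estimation the Phase II primary objective: "Estimate the ORR (complete + partial response) of the combination of oral 5-azacitidine and romidepsin".

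Four places bear on who is counted.

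- **Section 13.2, Phase II.** The two-stage rule refers to patients treated: "With 9 patients treated in the first stage, if 2 or fewer patients have a response within a stratum, the trial will be terminated". The final rule is a count of responders: "If 9 or fewer patients respond by the end of the second stage, the combination will not be considered for further study". The total is 24 patients.
- **Section 11.1.1.** "Patients who have received at least one day of therapy, and have had their disease re-evaluated will be considered evaluable for response". It then adds: "Patients who exhibit objective disease progression prior to the end of cycle 1 will also be considered".
- **Section 13.3, Phase I.** "Response rates will be based on all patients who receive at least one day of medication".
- **Section 13.3, Phase II and Exploratory Cohort.** Response is taken as best response by 4 cycles, and "Overall response rates will be estimated upon completion of the study along with exact 95% confidence intervals". No denominator is named.

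Section 11.2.5 defines the overall response rate as CR plus PR from each patient's best response and also names no denominator. The Phase II schema schedules "CT scans at the end of cycles 2 and 6", and the study calendar in section 10 agrees. With the 35-day cycle, the first scheduled scan falls at about day 70.

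**The concern.** The needed rule is written for a Phase I secondary endpoint and left out for the Phase II primary endpoint. An analyst who looks for a response population in Phase II finds only 11.1.1, and that differs from the base of the design in 13.2.

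The two differ for one kind of patient: someone who receives study drug, stops before the end of cycle 2 because of toxicity, withdrawal, death or clinical decline, and has neither a disease re-evaluation nor documented progression in cycle 1. Under 13.2 that patient is one of the 24 and has not responded. Under 11.1.1 the patient leaves the denominator. Such a patient cannot be recorded as a responder, so the removal can only push the ORR up.

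The trial is open-label with a single arm, and the ORR will be read against outside figures. If the denominator is settled after the data are seen, the reported primary estimate depends on that choice.

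**Working it through.** **1. The plan's own design figures.** Inputs from 13.2: null 25%, alternative 50%, stop at 2 or fewer of 9, reject at 9 or fewer of 24. With X1 ~ Bin(9, p) and X2 ~ Bin(15, p):

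- P(stop early) = P(X1 ≤ 2)
- P(go) = Σ over x = 3 to 9 of P(X1 = x) · P(X2 ≥ 10 − x)
- E(N) = 9 + 15 · (1 − P(stop early))

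| Quantity | Computed | Stated in 13.2 |
|---|---|---|
| P(go) at 25% | 0.0485 | 0.049 |
| P(go) at 50% | 0.805 | 80% power |
| P(stop early) at 25% | 0.601 | 0.60 |
| E(N) at 25% | 9 + 15 × 0.399 = 14.99 | 15 |

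The design reproduces. These figures treat every one of the 9 and 24 treated patients as a responder or a non-responder.

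**2. What the choice of denominator does to the estimate.** Let x be the number of responders among 24 treated, and m the number who are not evaluable under 11.1.1. None of the m is a recorded responder.

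- All treated: x/24
- Section 11.1.1: x/(24 − m), larger by the factor 24/(24 − m)
- Exact 95% interval for x out of n: lower limit is the 2.5% point of Beta(x, n − x + 1); upper limit is the 97.5% point of Beta(x + 1, n − x)

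Take x = 10, the smallest count that passes the final rule. The documents give no rate for m, so every row after the first rests on an assumption.

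| m (assumed) | ORR | Exact 95% interval |
|---|---|---|
| 0 | 10/24 = 41.7% | 22.1% to 63.4% |
| 1 | 10/23 = 43.5% | 23.2% to 65.5% |
| 2 | 10/22 = 45.5% | 24.4% to 67.8% |
| 3 | 10/21 = 47.6% | 25.7% to 70.2% |
| 7 (outer bound, see step 3) | 10/17 = 58.8% | 32.9% to 81.6% |

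Two missing patients add about 4 points to the ORR, and three add about 6.

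**3. A bound from the protocol's own background.** In section 7.2.2.4, the romidepsin-alone study in PTCL and other T-cell lymphomas reports 15/48 = 31% in all subjects and 15/34 = 44% in those with at least 2 cycles. The exact intervals are 18.7% to 46.3% and 27.2% to 62.1%. Fourteen of 48 subjects had fewer than 2 cycles; scaled to this trial, 24 × 14/48 = 7. This is an analogy and an outer bound. The 34 are a 2-cycle subset, whereas 11.1.1 would keep any of the 14 who had been re-evaluated or had progressed in cycle 1. The number of such subjects is not given.

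**4. What does not change.** With 24 treated and no replacement, both rules in 13.2 count responders. The count x is the same whichever denominator is reported, so the decision and the 0.049 stand.

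**The case against.** Several points on the other side are sound.

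- Section 11.1.1 never says that the ORR is divided by evaluable patients. Phase I uses an all-treated denominator alongside the same 11.1.1, so that definition does not fix the denominator by itself. This stands. It makes the defect an unstated denominator with two candidates, rather than two prescribed ones.
- Re-evaluation need not be a CT. Section 11 lists physical examination among the response methods, 11.1.3 accepts superficial lesions as measurable, and 5.6 asks for final-visit activities at discontinuation. Many early stoppers may therefore be evaluable, and m may be small. This also stands, and it is why no value of m is claimed.

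A reader might also infer more than the documents support.

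- **That the same data could give opposite decisions.** Nine responders with an assumed 7 missing give 9/17 = 52.9%, above the 50% target, yet 13.2 rejects the combination. But 13.2 rejects at nine responders whichever percentage is reported.
- **That the 0.049 error rate is inflated.** That would need unevaluable patients to be replaced until 9 and 24 evaluable ones were reached. No passage provides for replacement, and the synopsis and 13.2 fix accrual at 24.
- **That an interval lying above 25% counts as success.** Section 13.3 plans the interval for estimation only. Even with all treated, 10/24 passes the rule while its interval includes 25%.
- **That the romidepsin shift from 31% to 44% shows the interval would clear 25% here.** Adding back 3 of the 14 excluded subjects gives 15/37, with a lower limit of 24.8%. At this trial's size, 7/17 (18.4% to 67.1%) and 8/17 (23.0% to 72.2%) both include 25%.

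**Conclusion.** The point holds as a gap in the definition of the primary estimate. The design counts all treated patients, the only evaluability definition drops some of them, and the Phase II analysis paragraph chooses neither. Using 11.1.1 would bias the reported ORR upward by the factor 24/(24 − m). With 10 responders, that is about 4 to 6 points for 2 or 3 patients not re-evaluated, and the lower confidence limit moves from 22.1% to 24.4% or 25.7%.

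The direction follows from the definitions. The size rests on an assumed m, for which the documents give no figure. The go/no-go rule, the stated type I error and the power are unaffected. The denominator should be fixed because the affected quantity is the Phase II primary objective and the plan already contains the right rule for Phase I.

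**What to change.** In section 13.3, Phase II and Exploratory Cohort, add:

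> The ORR denominator is every patient given one or more days of study drug, as in Phase I. In Phase II the same patients are used for the stage 1 rule, the final rule and the exact 95% CI. Patients with no post-baseline response assessment count as non-responders and are not replaced. ORR in patients evaluable under 11.1.1 is supportive only.

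In section 11.1.1, add:

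> This definition does not set the Phase II ORR denominator; see 13.3.

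The cost is a short paragraph and one cross-reference. No patients are added, and the 2/9 and 9/24 boundaries, alpha and power stay as stated. The downside is that the reported ORR may be lower than an evaluable-only figure: 41.7% instead of 47.6% in the example with 3 missing.

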### ***Exploratory Cohort***

A total of 10 patients with GC-derived lymphoma will be accrued.

We estimate an average accrual of 1-2 patients per month, with a goal of completing accrual within 12 months.

### **13.3 Analysis of Secondary Endpoints**

#### **Phase I**

The maximum number of cycles will be described by dose level.

The number of delays >7 days will be described at the MTD.

ORR as defined by the guidelines of the International Harmonization Project Group 2007 Revised Response Criteria, and will be tabulated by dose level. (See Section 11.2.1.) Response rates will be based on all patients who receive at least one day of medication.

#### **Phase II and Exploratory Cohort**

Primary Objective: To estimate ORR defined as best response by 4 cycles.

Disease and patient characteristics at baseline will be summarized using descriptive statistics. For qualitative variables, frequency distributions and proportions will be provided; for quantitative variables, summary statistics (e.g., mean, median, quartiles, standard deviations, etc) and graphical displays (e.g., box plots). Overall response rates will be estimated upon completion of the study along with exact 95% confidence intervals.

